Primary SA1: Determine whether 24 weeks of GnRH_{AG} therapy causes a decline in physical activity when compared with placebo. Change in physical activity energy expenditure (PAEE) from baseline will be measured after 12 (secondary outcome) and 24 wk (primary outcome) of GnRH_{AG} vs placebo therapy. PAEE will be the difference between total daily EE (TEE) measured by the doubly-labeled water technique (DLW) and sleeping EE (SEE) measured by indirect calorimetry, adjusted for the thermic effect of feeding (TEF).¹⁴

H1: PAEE will decrease significantly after 12 and 24 weeks of GnRH_{AG} therapy when compared with placebo.

Secondary SA2: Determine the effects of gonadal function on multiple components of energy expenditure under free-living (DLW) and controlled (metabolic chamber) conditions, including 1) 24-h TEE measured by DLW, and 2) resting EE (REE), SEE, and TEF measured by indirect calorimetry in a metabolic chamber.

H2: When compared with placebo, GnRH_{AG} therapy will cause a decrease in TEE. The relative contributions of REE, SEE, TEF, and PAEE to the decline in TEE will be evaluated.

Secondary SA3: Determine whether the disruption of energy balance in response to GnRH_{AG} therapy leads to unfavorable changes in biomarkers of disease risk, including adiposity, insulin resistance, and inflammation. This will include the measurement of biomarkers in adipose tissue samples.

H3: When compared with placebo, GnRH_{AG} therapy will cause increases in adiposity, insulin resistance, and fasted serum inflammatory cytokines.

Secondary SA4: Because programmed exercise mitigates metabolic consequences of gonadectomy in animals, we will determine whether the bioenergetic and metabolic consequences of GnRH_{AG} in women can be

mitigated through a programmed, supervised exercise intervention (GnRH_{AG} vs GnRH_{AG}+exercise).

H4: Programmed exercise will attenuate the decrease in TEE and the increases in adiposity, insulin resistance, and inflammatory cytokines.

Exploratory Aim: To evaluate the effects of chronic sex hormone suppression and exercise on arterial stiffness and endothelial function. This preliminary data will be used for a new grant application examining the effects of exercise on modulating vascular function in E2-deficient women.

2. Research Strategy

2.a. Significance

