
2.d. Research methods

2.d.1. Overview

This will be a randomized, double-blinded (to the extent possible), placebo-controlled intervention to determine whether the suppression of ovarian function with GnRH_{AG} disrupts energy balance by causing a decrease in PAEE. Secondary aims are to determine the effects of the suppression of ovarian function on other components of energy expenditure and on biomarkers of disease risk and whether the consequences of GnRH_{AG} can be mitigated through programmed exercise. Participants will be women who are nearing the menopausal transition based on age (42-52 y) but have normal menstrual cycle function. They will be randomized to receive monthly injections of placebo or GnRH_{AG} (leuprolide acetate, 3.75 mg) for 24 weeks. Women who receive GnRH_{AG} will be further randomized to no exercise or a supervised exercise program. Thus, the 3 treatment arms are: placebo, GnRH_{AG}, GnRH_{AG}+exercise. Although a 2x2 study design (placebo vs drug; no exercise vs exercise) was considered, this was not feasible given the resources available under the grant mechanism.

2.d.2. Outcome variables

The primary outcome (Aim 1) will be PAEE after 24 weeks of intervention. PAEE will be the difference between TEE measured by DLW and SEE and TEF, measured by indirect calorimetry. It will be assessed at baseline and after 12 and 24 weeks of intervention. The **rationale** for PAEE as the primary outcome is the dramatic decrease in PA in response to OVX in laboratory animals (Fig 1), which could be a primary trigger for subsequent changes in adiposity and metabolic function. This will be the first controlled intervention trial to determine whether an objective measure of PA decreases in response to the suppression of ovarian function in women. GnRH_{AG} therapy for 4 months or longer increases fat mass and decrease fat-free mass (FFM).^{9,10,36} One concern is that women may begin to adopt compensatory behavioral changes (e.g., decreased food intake, increased physical activity) if changes in body composition are sensed. Thus, the greatest **biologically-mediated** decrease in PAEE may occur at the intermediate testing interval (12 weeks), before measurable changes in body composition are expected to occur; this will be the primary study endpoint.

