Chamber stay. Participants will report to the CTRC at 0700h after an overnight fast. A urine sample for DLW will be obtained, if necessary. An IV catheter will be positioned in an antecubital vein and a fasted blood sample will be obtained. Participants will enter the chamber at 0800h. A reclining chair will be positioned next to the port in the chamber through which blood samples are obtained. Participants will rest for the first hour. At 0900h, they will drink a 75-g glucose beverage and remain semi-recumbent for the next 2 hours for the TEF measurement. To mimic typical activity outside the calorimeter, two 30-min bouts of treadmill walking at 3 mph will be performed at 1500h and 1630h. This activity should produce a physical activity level (PAL; TEE/REE) of ~1.5 (unpublished observations, [name] and [name]). All urine will be collected and analyzed for urine nitrogen, urea nitrogen, and creatinine for substrate oxidation calculations. Core temperature will be measured during the chamber stay using an ingestible thermistor capsule (length 23 mm, diameter 8.6 mm) and a VitalSense telemetric monitor. TEE will be calculated as previously described.⁵³ Stepping EE will be measured during the exercise bout. SEE will be measured from 0100h to 0400h.⁸¹ Pre-study diet and exercise are known to affect 24-h fat oxidation.^{82,83} Subjects will be asked to refrain from structured exercise the day before the chamber stay. Diet will not be controlled because of the possibility that energy intake (and possibly macronutrient preference) is influenced by ovarian function. The energy composition of the diet for the chamber stay will be 30% fat, 55% carbohydrate, and 15% protein, with the 75g glucose beverage accounting for breakfast and about 25% of total energy needs, while both lunch and dinner will each account for about 30-35% of total energy needs. 'Extra' calories will be provided in the form of a snack box that participants will have free access to from the time the lunch meal is delivered until lights out. Participants will be instructed to eat what they want and that it is not necessary to eat all the food provided. This approach may provide insight on whether the suppression of ovarian function promotes hyperphagia. Data from each calorimeter stay will be evaluated for state of energy balance.

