The **rationale** for the chamber stay is to **1)** obtain a prolonged measure of basal metabolic rate for the calculation of PAEE, **2)** obtain a measure of TEE under controlled conditions, **3)** determine whether TEF is influenced by GnRH_{AG}, and **4)** determine whether EE during a specific physical task (stepping activity) is influenced by GnRH_{AG}. PAEE will be the difference between TEE measured by DLW (adjusted -10% for TEF) and SEE measured during the chamber stay, as previously described.¹⁴ The OGTT will be performed in the calorimeter to avoid a separate visit for participants and to assess whether the TEF is influenced by GnRH_{AG}.⁸⁴

Blood samples during the chamber stay. Blood samples will be obtained before and 30, 60, 90 and 120 min after glucose ingestion. These will be used for the measurement of insulin resistance (product of the glucose and insulin areas under the curve) and inflammatory cytokines (IL-6, hsCRP) for **SA3**. The assays will be performed by the CTRC core laboratories. The extent to which changes in disease risk could be explored was limited by the resources available under the P50 mechanism. Measures of insulin resistance and mild chronic inflammation were selected because of the prominent role these factors play in metabolic dysfunction.⁸⁵

Chamber stay alternative. Heavy use of the metabolic chamber for multiple research protocols has created scheduling difficulties. Subjects who cannot complete the 24-hr metabolic chamber stay in a timely manner will be offered the option of completing this alternative approach. Subjects will report fasted to the CTRC at 7:00am and will have vitals measured and an IV catheter inserted for the OGTT. At 7:30am they will consume a 75-g glucose beverage and remain semi-recumbent for the next 3 hours for the OGTT and TEF measurements. Blood samples will be drawn before and 30, 60, 90 and 120 min after glucose ingestion. The IV will be removed after the last blood sample. TEF will be measured through indirect calorimetry using the ventilated

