hood method (Parvo Medics metabolic cart). Measurements will be taken at 30-minute intervals, and each measurement will last for approximately 10 minutes. Subjects will remain in bed for the duration of the measurements, except to use the bathroom. If the subject needs to use the bathroom, this will be done immediately after a measurement, with the patient then returning to bed as soon as possible. PAEE will be calculated exactly as it is being done in chamber studies, TEE (DLW) - (RMR + TEF).

Tissue biopsies. This research project is a component (Project I) of a Specialized Center of Research (SCOR) on Sex Differences (PI, [name]) sponsored by the NIH Office of Research on Women's Health. The topic of the UCAMC SCOR is *Bioenergetic and Metabolic Consequences of the Loss of Gonadal Function*. **SCOR Project II** (PI, [name]) is a preclinical study (animals) of *Effects of Pre-existing Obesity on Consequences of the Loss of Ovarian Function*. **SCOR Project III** (PI, [name]) is a basic study (animals) on *Sex Hormones Differentially Regulate Production of Distinct Adipocyte Populations*. The tissue samples to be obtained from participants in **Project I** (below) will address specific aims from **Project I** as well as **Projects II and III**.

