Limitation of the follow-up testing schedule. For women assigned to the placebo treatment arm, the follow-up tests will not necessarily occur at the same point in the menstrual cycle as the baseline test. Testing will occur during specific time intervals (weeks 10-12, 22-24) to be consistent with the GnRH_{AG} arms. Because this may increase the variance of changes in bioenergetics in the placebo arm, the sample size calculations relied on conservative assumptions (e.g., ability to detect a 25% change in PAEE; use of $\rho = 0.9$; power of 95%).

2.d.10. Data analysis

General Analysis Plan. Data analysis will occur in 4 steps: **1)** Descriptive analyses (including boxplots, scatterplots, profile plots to examine change over time) will be conducted for quality assurance and to assess need for data transformation; **2)** demographic and baseline characteristics of the groups will be compared; **3)** primary and secondary analyses will be completed; and **4)** findings will be assessed for their robustness to issues including the effects of any imbalances in important baseline covariates and the effects of missing data.

Primary Analysis. The primary analysis (**SA1**) will be an intention-to-treat comparison of the differences in the change in PAEE measured after 12 weeks of placebo or GnRH_{AG} therapy. This comparison will be conditioned on the stratification variable, age group (40-46, 47-60y). Statistical inference regarding the difference between treatment groups will be based on the estimated coefficient for a treatment group indicator variable in a linear regression model with 24-week change from baseline as the response variable, and explanatory variables,

including treatment group, age group, and baseline PAEE; the latter is included to improve the precision/power of the inference about treatment differences. The conclusion about statistical significance will be drawn from the linear contrast comparing the placebo and GnRH_{AG} groups.

Secondary Analyses. To address **SA2** and **SA3**, 24-week differences in other outcome measures (24-h TEE, REE, SEE, TEF, PA by accelerometry, measurement of biomarkers in adipose tissue samples, glucose and insulin response to OGTT, serum concentrations of

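### H2's split of the TEE change is undefined as written: REE and SEE overlap as basal terms, and the PAEE formulas disagree on how TEF is removed

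*Combined protocol and SAP*

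**What the plan says.** **H2.** Section 1, SA2 lists TEE by DLW and "resting EE (REE), SEE, and TEF measured by indirect calorimetry in a metabolic chamber". H2 then states that "The relative contributions of REE, SEE, TEF, and PAEE to the decline in TEE will be evaluated".

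**PAEE is described in four places.**
- Section 1, SA1: DLW TEE minus SEE, adjusted for TEF. The adjustment is not spelled out.
- Section 2.d.2: "PAEE will be the difference between TEE measured by DLW and SEE and TEF, measured by indirect calorimetry".
- Section 2.d.9.1, rationale for the chamber stay: "PAEE will be the difference between TEE measured by DLW (adjusted -10% for TEF) and SEE measured during the chamber stay". This cites the same reference as SA1.
- Section 2.d.9.1, chamber stay alternative: "PAEE will be calculated exactly as it is being done in chamber studies, TEE (DLW) - (RMR + TEF", with the bracket closing there.

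**Basal term.** The rationale for the chamber stay gives as its first purpose to "obtain a prolonged measure of basal metabolic rate for the calculation of PAEE", and the term then used is SEE. The alternative puts RMR in that slot.

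**TEF.** In the chamber, "they will drink a 75-g glucose beverage and remain semi-recumbent for the next 2 hours for the TEF measurement". In the alternative, hood readings are taken over 3 hours after the same drink. Neither description scales the result to a day.

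**Analysis.** Section 2.d.10 models "24-week differences in other outcome measures (24-h TEE, REE, SEE, TEF, PA by accelerometry" and further outcomes one at a time. It gives no method for relative contributions.

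**The concern.** Relative contributions to a decline suggest parts of a whole. For that, the parts must not overlap, must add to the change in TEE, and must be on the same daily scale. H2's list fails the first condition because REE and SEE measure much the same thing. Whether it meets the second depends on which PAEE formula is used. Measured TEF fails the third.

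The TEF rule also reaches the primary outcome. If a tenth of TEE is always removed as TEF, part of any change in activity or basal rate can leave or enter PAEE without TEF having moved. At stake are the interpretation of H2 and, to a smaller degree, the size of the primary effect and of the exercise contrast.

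**Working it through.** **Inputs.** From Section 2.d.4: baseline PAEE 800 kcal, SD 330, expected effect -25% (200 kcal/d), correlation 0.90, 15 per group. From Section 2.c: REE changes of -42 and -71 kcal/d in the acute study, and a hypothesised fall of 40 to 50 in the ongoing study (midpoint 45 used). From Section 2.d.7: exercise goal of about 1400 kcal/wk. Assumptions: REE and SEE change equally; alpha is two-sided.

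**1. The plan's own figure.** No figure is given for the H2 split. The sample size does reproduce: SD of change = √(2 × (1 - 0.90)) × 330 = 147.6, stated as 148. With 15 per group and a difference of 200, power is 0.959 (normal) or 0.946 to 0.951 (t), against the stated 95%.

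**2. Algebra.** Let A, B and F be the true changes in activity, basal expenditure and daily TEF, so ΔTEE = A + B + F. Let ΔSEE = B.
- 10% rule: ΔPAEE = 0.9 × ΔTEE - ΔSEE = A + (F - 0.1 × ΔTEE). The implied TEF term is 0.1 × ΔTEE whatever F is.
- SEE and TEF subtracted: ΔPAEE = ΔTEE - ΔSEE - ΔTEF, which equals A only if the TEF used is daily TEF.

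**3. Adding H2's terms.** Take A = -200, B = -45, F = 0, so ΔTEE = -245.
- 10% rule: PAEE = -220.5 + 45 = -175.5 (71.6%), implied TEF -24.5 (10.0%), SEE -45 (18.4%); total 100%.
- Add REE -45: total -290, and 290/245 = 118.4%. With B = -42 the total is 284/242 = 117.4%; with B = -71 it is 342/271 = 126.2%.
- 10% rule PAEE with a measured TEF change of 0 and SEE only: -220.5/-245 = 90%.
- Daily TEF subtracted, one basal term: PAEE -200 (81.6%), SEE -45 (18.4%), TEF 0; total 100%.

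**4. Effect of the 10% rule on PAEE.** Take A = -200, B = 0, with F varied by assumption (kcal/d):

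| F | ΔTEE | Recorded ΔPAEE (0.9 × ΔTEE) | Recorded minus true | ΔTEE - ΔSEE |
|---|---|---|---|---|
| 0 | -200 | -180 | +20 | -200 |
| -20 | -220 | -198 | +2 | -220 |
| -22.2 (10% of ΔTEE) | -222.2 | -200 | 0 | -222.2 |
| -40 | -240 | -216 | -16 | -240 |
| +20 | -180 | -162 | +38 | -180 |

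In the first three rows, where F lies between 0 and 10% of ΔTEE, the third and fifth columns bracket the true -200. In the last two they do not. A basal-only fall of 45 gives ΔPAEE = -40.5 + 45 = +4.5 with no change in activity. The exercise goal is 1400/7 = 200 kcal/d; if activity alone rises by that amount, 0.9 × 200 = 180 is recorded.

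**5. Does measured TEF solve it?** The drink is the same at every visit, so a change in daily TEF caused by eating more or less would be largely invisible to it. In the second row, if the drink response is unchanged, subtracting it leaves ΔPAEE = -220, which is 10% too large. The 10% rule gives -198.

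**The case against.** The strongest reply is that the 10% rule is only one of the stated formulas. Section 2.d.2 subtracts TEF measured by calorimetry, and the chamber alternative subtracts RMR and TEF with no fixed percentage. With a daily TEF and one basal term the parts add to 100%. This stands. A reader might infer that H2's contributions cannot be derived at all; they are undefined as written, but can be derived once one formula and one basal term are fixed.

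A reader might also infer that H2 would report a TEF share of exactly 10%. The documents do not support this. TEF is a measured SA2 outcome, Section 2.d.10 analyses it directly, and nowhere is a tenth of TEE named as H2's TEF result. Nor does any section say that four shares will be summed, so the 118% shows what happens if they are.

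A third inference would be that PAEE loses between 0 and 10%. That is not a bound. Section 2.a reports intake falling by about 30% in the natural-menopause cohort, Section 2.d.2 foresees reduced intake, and the chamber stay looks for hyperphagia, so the error can take either sign.

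Finally, a shift of 20 to 25 kcal/d is small beside an SD of change of 148. That is fair. It is nevertheless a systematic shift, about a tenth of the planned difference, and more participants would not remove it.

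**Conclusion.** The point holds in limited form. H2's four terms are not a valid partition of the TEE change: counting both REE and SEE takes the total to about 117% to 126% in the examples, assuming they fall equally. The PAEE formulas in Sections 1, 2.d.2 and 2.d.9.1 need reconciling. Under the 10% rule the error in PAEE change is F - 0.1 × ΔTEE: zero when TEF changes by 10% of the TEE change, a 10% loss of an activity-only change when TEF is constant, and larger or reversed otherwise. Measured TEF does not settle the matter, because it is an unscaled 2-h or 3-h response to one fixed drink. Women on the chamber alternative have no overnight SEE, so their SEE share does not exist.

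A reader might go on to conclude that the trial is underpowered. That does not follow: the 200 kcal/d target is set on the PAEE scale, and the stated power reproduces.

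**What to change.** 1. Reconcile the PAEE definitions in SA1, Section 2.d.2 and both parts of Section 2.d.9.1 to one formula, and state the TEF assumption it makes.
2. Specify H2 in Section 2.d.10 with one basal term: change in TEE = change in SEE + change in (TEE - SEE), the second part being activity plus TEF.
3. Report REE separately, and measured TEF separately as a percentage of the drink's energy.
4. Pre-specify a sensitivity analysis of the primary outcome using change in TEE minus change in SEE. State that, together with the 10% rule, it brackets true activity change only when the TEF change lies between 0 and 10% of the TEE change.
5. For women on the chamber alternative, use RMR as the basal term at both baseline and follow-up. RMR is scheduled at Visit 1 for all women and repeated at both follow-up intervals.

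The cost is analysis-plan wording and one additional model on data already scheduled for collection. The downside is that H2 claims fewer separate components. The sensitivity analysis also rests on an assumption (no TEF change), which is why it should be read beside the 10% rule and not in place of it.

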Injections will be administered in a blinded manner, but participants on GnRH_{AG} will likely know their drug assignment because of the induction of amenorrhea. For this reason, volunteers will not be informed during the consenting process that the primary aim of the study is to determine whether GnRH_{AG} causes a decline in physical activity (i.e., such knowledge may change behavior). Rather, women will be informed that the loss of normal ovarian function may alter how the body uses energy or have other metabolic effects. Participants who do not tolerate GnRH_{AG} therapy can refuse further treatment after each monthly dosing. Among the first 64 premenopausal women treated with GnRH_{AG} in the PI's ongoing study (AG018198), this occurred only once. Participants who undergo at least 2 months of therapy but not 6 months will be asked to undergo testing at the end of their final month of therapy. Should this occur, data analyses will include covariate analysis to adjust for duration of intervention.

Exercise intervention. If the loss of ovarian function generates a biological drive toward sedentary behavior, it may be possible to override this through programmed exercise. In laboratory animals, E₂ add-back and programmed exercise (i.e., treadmill running) each prevented, to a large extent, the OVX-related changes in body composition and biomarkers of disease risk (Fig 5).²⁵⁻²⁹ The intent of **SA4** is to determine whether programmed exercise can offset the decline in PAEE in response to GnRH_{AG} (PAEE: GnRH_{AG} < GnRH_{AG}+exercise). Although it may seem logical to assume this will occur, it is possible that programmed exercise will cause a further decrease in other physical activities, such that programmed exercise produces no net gain in PAEE.

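### Women who stop injections are not asked to return for the weeks 10-12 and 22-24 tests, so the intention-to-treat contrast on 24-week PAEE change would rest on off-schedule, on-treatment values for some women and probably none for the earliest stoppers

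*Combined protocol and SAP*

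**What the plan says.** Section 2.d.7 (Drug intervention) allows stopping after any dose: "Participants who do not tolerate GnRH_{AG} therapy can refuse further treatment after each monthly dosing". It then provides: "Participants who undergo at least 2 months of therapy but not 6 months will be asked to undergo testing". The timing follows treatment and not the calendar, because these women "will be asked to undergo testing at the end of their final month of therapy". For such cases, "data analyses will include covariate analysis to adjust for duration of intervention". The section makes no provision for women who stop before two months.

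Section 2.d.9.2 places the follow-up visits in weeks 10-12 and 22-24 of the intervention. It does not say whether women who have stopped injections are still expected.

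Section 2.d.10 describes the primary analysis as an "intention-to-treat comparison of the differences in the change in PAEE measured after 12 weeks", but bases inference on a treatment coefficient "in a linear regression model with 24-week change from baseline as the response variable". Section 2.d.2 states "The primary outcome (Aim 1) will be PAEE after 24 weeks of intervention", and aim SA1 agrees. The same section later calls 12 weeks the primary study endpoint. Missing data appear only in a general robustness step with no method named.

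**The concern.** An intention-to-treat contrast at week 24 needs a week-24 value, or an honest attempt to get one, from every randomised woman. Here the request for a test depends on treatment received. A woman who stops after four injections would contribute a value near week 16 while still on drug. A woman who refuses her second injection would probably contribute only a baseline. The plan links refusal to not tolerating GnRH_AG, so the gap is likely to fall more on the active arms than on placebo, and on women with more oestrogen-deficiency symptoms. Section 2.d.14 names sleep disturbance from such symptoms as a possible mediator of lower PAEE, so these women's outcomes may be informative.

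The stated remedy does not close the gap. Duration of intervention is determined after randomisation and is affected by treatment. Adjusting for it does not recover the week-24 value under assignment, and it can disturb the randomised comparison.

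**Working it through.** **The plan's own figure.** The inputs in section 2.d.4 are SD 330 kcal, correlation 0.90, a 200 kcal/d difference, 15 per group and alpha 0.05.
- SD of change = √(2 × (1 − 0.90)) × 330 = 147.6, stated as 148.
- Two-sided t contrast with 42 error degrees of freedom: power 0.951, against the stated 95%. The figure reproduces and is not in dispute.

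**When each stopper would be tested.** Section 2.d.9.1 gives six injections at 4-week intervals, so therapy covers 4k weeks after k injections.

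| Injections received | End of last month | Test requested by 2.d.7 | Relation to scheduled tests |
|---|---|---|---|
| 1 | week 4 | none stated | neither window addressed |
| 2 | week 8 | week 8 | 2-4 weeks before the weeks 10-12 test |
| 3 | week 12 | week 12 | coincides with the weeks 10-12 test |
| 4 | week 16 | week 16 | 4-6 weeks after the first window, 6-8 before the second |
| 5 | week 20 | week 20 | 8-10 weeks after the first window, 2-4 before the second |

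None of these gives a week-24 value. Section 2.d.9.2 also cites advice that serial DLW measurements be at least 10 weeks apart. Apart from the week-12 coincidence, no end-of-therapy DLW test keeps that distance from both scheduled tests.

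**Which time point.** With 24-week change as the response, every row is affected. On the 12-week wording in 2.d.2 and 2.d.10, women with three or more injections already have their test, so the gap is mainly the first two rows.

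**What the planned models do.** The regression needs a change score. The mixed model in 2.d.10 conditions on baseline. Neither uses a woman with a baseline alone.

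**Size.** If a share p of the GnRH_AG arm lacks a usable week-24 value, and those women differ from the rest by d in PAEE change, the arm mean shifts by p × d. The documents give no d, so 100-200 kcal/d is an assumption. The placebo arm is taken as complete.

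| Rate used | p | Women of 22 | Shift, d = 100 | Shift, d = 200 |
|---|---|---|---|---|
| Refusal for intolerance, 1 of 64 (2.d.7) | 1.6% | 0.34 | 1.6 kcal/d | 3.1 kcal/d |
| Exact upper 95% limit of 1 of 64 | 8.4% | 1.8 | 8.4 | 16.8 |
| All losses, 7 of 64 (2.c) | 10.9% | 2.4 | 10.9 | 21.9 |

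Against the 200 kcal/d target, the first row is 0.8-1.6% and the last 5.5-10.9%.

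**Effect of testing everyone.** Suppose the on-drug effect is 200 kcal/d and stoppers return to zero by week 24. The intention-to-treat effect is then 200 × (1 − k/22), where k is now the number of stoppers in the arm: 191, 182 and 173 kcal/d for k = 1, 2 and 3. With 22 per group all measured and SD 148, power is 0.99, 0.98 and 0.97. The issue is which effect is estimated, more than power.

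**The case against.** Several points on the other side stand.

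- **The text is silent, not prohibitive.** A reader might infer that early stoppers are barred from testing, or that the end-of-therapy test is declared to replace week 24. Neither is stated. The first is inferred from the two-month lower limit and silence elsewhere; the second from the duration covariate.
- **Something is planned.** The duration covariate and the missing-data step exist. The criticism is that the first is the wrong tool for this contrast and the second names no method.
- **Analysis is not powerless.** A reader might infer that no method could retain a woman with only a baseline. That is true of the planned models. Multiple imputation, or a longitudinal model with baseline among the outcomes, could keep her under stated assumptions, and the monthly activity-monitor data might help. Neither is planned, and assumptions are weaker than a measurement.
- **Intolerance was rare.** The sponsor's earlier study saw one refusal among 64 women, and six of its seven losses were for time or family reasons. But that study lasted five months and gave some women E2 add-back, so its rate may understate intolerance here.
- **A mechanistic study may want on-drug values.** Section 2.d.7 says menses typically return within 2-3 months of stopping, so late values in early stoppers may reflect recovered ovarian function. This is a fair reason to report an on-treatment analysis, but not to label it intention-to-treat.

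**Conclusion.** The point holds as a mismatch between the outcome-testing rule in 2.d.7 and the intention-to-treat contrast in 2.d.10. It is fullest on the 24-week reading and limited mainly to women stopping before the weeks 10-12 test on the 12-week reading.

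The likely size is small: about 2-3 kcal/d at the documented intolerance rate and about 11-22 kcal/d at the total loss rate, both resting on the assumed 100-200 kcal/d difference. The direction is unknown. On-drug values would overstate the effect if stoppers recover; losing the women with the largest declines would understate it.

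A reader might infer a larger bias by supposing that several of 22 women stop before two months, or by reading the attrition allowance (22 enrolled for 15 needed, so 7 of 22) as a forecast of intolerance. The documents support neither. Three of 22 is 13.6%, above the 8.4% upper limit for refusal at any time, and the allowance covers attrition of every kind.

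The change is still worth making: it is cheap, and a value not collected cannot be recovered later.

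**What to change.** Change the outcome-collection wording only; dosing and the right to stop are untouched.

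1. In 2.d.7, state that every randomised woman is asked to attend the weeks 10-12 and 22-24 outcome tests whatever her treatment status, and is analysed in her assigned arm.
2. Keep the end-of-therapy test as an additional on-treatment value that does not replace week 24. Where the 10-week DLW spacing in 2.d.9.2 would be broken, it gives way to the scheduled test. On the timings above, the DLW part would nearly always give way.
3. Take the duration covariate out of the primary model and use it in a labelled on-treatment sensitivity analysis.
4. Settle the 12- versus 24-week wording in 2.d.2 and 2.d.10, since it decides which women are affected.

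The cost is a short text change and a few tests after stopping, within a visit schedule already planned for 66 women. Those tests are burdensome, and section 2.d.12 says chamber availability limits accrual; the chamber alternative in 2.d.9.1 may ease this. The scientific cost is some dilution of the mechanistic effect, which the on-treatment sensitivity analysis addresses. The consent pages are not in the public document, so whether consent already covers testing after stopping should be checked.
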